4. ANALYSIS POPULATIONS

4.1 Efficacy Population

- The modified Intent to Treat (mITT) population will include all randomized patients who receive study drug and have at least one non- missing NPRS assessment within the primary endpoint timeline (12-96 hours, inclusive). In addition to the primary analysis of the primary endpoint, all efficacy analyses will be performed using this population. Analyses will be performed on subjects using their randomized treatment group.
- All **Randomized Subjects**: All participants who are successfully screened and randomized.

For all efficacy analyses, subjects will be analyzed based on the mITT population.

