#### **Study Populations**

For efficacy analysis, modified intent to treat (mITT) population will include all randomized and treated patients with at least one post-injection pain score. All efficacy analyses will be performed using this population. Analyses will be performed on subjects using their randomized treatment group.

The Per Protocol (PP) population will include all subjects in the mITT population with no major protocol violations. The primary efficacy variable will also be analyzed using this population.

The Safety population will include all subjects exposed to any amount of study drug. All safety analyses will be performed using the safety population.

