#### **5.4.3 Handling of Participant Exceeding Allowed Rescue Medication**

Subjects who exceed limit of allowed rescue medication, considered noncompliance with the protocol specified in [Section 5.4.1](#) due to lack of efficacy, will be followed, not early terminated, with regard to all safety assessments per protocol. They at all subsequent visits will be asked to complete protocol-specified assessments, with the exception of efficacy assessments as follows:

- NPRS
- NPRS-A
- Collection of take-home pain assessment diary

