### **10.3 Analysis Populations**

The modified Intent to Treat (mITT) population will include all randomized patients who receive study drug. All efficacy analyses will be performed using this population. Analyses will be performed on subjects using their randomized treatment group.

The Per Protocol (PP) population will include all subjects in the mITT population with no major protocol violations. The primary efficacy variable will also be analyzed using this population.

The Safety population will include all subjects exposed to any amount of study drug. All safety analyses will be performed using the safety population.

Analyses of using the PP and Safety populations will analyze subjects according to the treatment received. In the event that the subject receives the wrong treatment, they will be excluded from the per protocol population.

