Rescue medication when needed is a maximum of 5 doses of 50 µg IV Fentanyl (up to 250 µg total) during the first 120 minutes after post-anesthesia care unit (PACU) arrival. After the first 120 minutes have elapsed, subjects during confinement may only receive oxycodone 5 mg every 4 hours, PRN. Following discharge from the hospital, subjects may use 500 mg acetaminophen PRN, a maximum of 6 times per day (not to exceed 3 g total dose in 24 hours). Subjects will be instructed not to take rescue medication until their pain reaches at least a moderate intensity, and to complete an entry in their Pain Assessment Diary prior to taking rescue medication. All post-discharge rescue medication usage must be recorded in the Rescue Medication Diary. Subjects' rescue use will be captured on the Rescue Medication eCRF during the Inpatient portion of the study and in the Subject Rescue diary after discharge until Day 29. If additional rescue medication, other than the study rescue medications, appear on the concomitant medications page and can be identified, those medications will also be included in summaries as described below.

The summary will include all rescue taken by subjects regardless of their status (discontinued from efficacy or not).

Total amount of opioids (MEQ) used during the first 96 hours will be summarized overall (0-96hrs). [Table 7-1](#) will be used to calculate the morphine milligram equivalents (MEQ) for each medication. The total opioid consumption for each day for each subject will be calculated as the sum of the MEQs of all of the medications taken on that day. For example, if a subject takes 5 MEQ morphine on Day 1 and Day 2, and 10 MEQ of Oxycodone on Day 2, the total consumption for Day 1 is 5 MEQ, and the total consumption for Day 2 is 15 MEQ. Subjects that take no opioids on a day will have a total opioid consumption value of zero for that day.

Table 7-1 Table of Morphine Milligram Equivalents
(from cdc.gov/drugoverdose/pdf)

[figure not shown]
Opioid (Doses in mg/day)	Conversion Factor
Codeine	0.15
Fentanyl transdermal (in mcg/hr)	2.4
Hydrocodone	1
Hydromorphone	4
Morphine	1
Oxycodone	1.5
Oxymorphone	3

Total dose of Oxycodone used during the first 96 hours and the number of doses of Oxycodone will both be summarized separately. Summaries will be shown both for overall (0-96hrs). Total Oxycodone use will also be presented graphically overall and by cohort.

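### SAP 4.1 limits mITT to subjects with an NPRS score at 12–96 h, narrower than either protocol definition; an early treatment failure can leave the PGA and, as worded, the rescue-use summaries

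*SAP*

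**What the plan says.** The documents define mITT in three ways.

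- Protocol 10.3: "The modified Intent to Treat (mITT) population will include all randomized patients who receive study drug". No pain score is needed.
- Protocol Summary, Study Populations: "all randomized and treated patients with at least one post-injection pain score".
- SAP 4.1: randomized, dosed, and at least one non-missing "NPRS assessment within the primary endpoint timeline (12-96 hours, inclusive").

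The SAP then fixes the scope: "For all efficacy analyses, subjects will be analyzed based on the mITT population". SAP section 12 lists no change to the population and leaves any deviation to the study report.

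Protocol 5.4.3 covers subjects who exceed the rescue limit. It treats this as noncompliance "due to lack of efficacy, will be followed, not early terminated, with regard to all safety assessments per protocol". At later visits they "complete protocol-specified assessments, with the exception of efficacy assessments as follows": NPRS, NPRS-A and collection of the pain diary. PGA and rescue records are not on that list, so they continue.

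SAP 7.3.4 says of rescue medication: "The summary will include all rescue taken by subjects regardless of their status (discontinued from efficacy or not"). SAP 7.1.1 imputes nothing in the AUC for early dropout; the only fill-in is a four-hour carry-forward of a pre-rescue score.

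**The concern.** The added SAP condition depends on something that happens after randomization and that treatment can affect. SAP 7.3.4 already sets a rescue cap in the first 120 minutes after PACU arrival, so the limit can be reached well before hour 12. A subject who passes it and stops scoring by then has no score in the window and is excluded because pain was not controlled.

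For PGA and rescue use the excluded data exist. Rescue use is named in the efficacy objective, and it is where early failure shows most directly. Dropping such subjects makes the arm in which they occur look better controlled than it was. SAP 4.1 and SAP 7.3.4 also give a programmer two instructions for rescue use, with no rule on which prevails. SAP section 3 ranks specific sections above its own general conventions, but does not rank 4.1 against 7.3.4.

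**Working it through.** **Planning figures.** Some are reused below, so I checked that they cohere. Protocol 10.5 gives 22 per arm, one-sided alpha 0.05, difference 110, SD 170 and about 67% power. The noncentrality is 110 / (170 × √(2/22)) = 110 / 51.26 = 2.15. With 42 degrees of freedom the one-sided t-test has 68.0% power, which agrees. The present point does not rest on that power.

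**Step 1: membership.** Take a dosed subject who exceeds the rescue limit and stops NPRS before hour 12.

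| Definition | Score required | Subject in mITT? |
|---|---|---|
| Protocol 10.3 | none | yes |
| Protocol Summary | any after injection | yes, if scored at least once |
| SAP 4.1 | NPRS at 12–96 h | no |

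**Step 2: what the SAP wording costs, by endpoint.**

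- AUC12-96: no assessment falls in the window. A four-hour carry-forward from before hour 12 covers less than 4 of the 84 hours. The value is lost under all three definitions, so the shift attributable to the mITT wording is zero.
- AUC0-24 to AUC0-96 and early NPRS-A: scores before hour 12 exist and are dropped, but any AUC from them is truncated.
- PGA at 96 h and Days 8, 15 and 29: still collected, dropped by SAP 4.1.
- Rescue use: still collected, dropped by SAP 4.1, kept if SAP 7.3.4 governs.

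**Step 3: size for PGA.** Planned Cohorts 1–3 have 1 + 3 = 4 active subjects per dose and 3 × (2 + 2) = 12 placebo subjects, 24 in all. The SAP reports 23 dosed; the actual split is not shown. One exclusion removes 1/4 = 25% of a dose group or 1/12 = 8.3% of pooled placebo. Assume that subject, and no other, rates control as Poor at 96 h. The reported proportion goes from 1/4 = 25% to 0/3 = 0% in a dose group, or from 1/12 = 8.3% to 0/11 = 0% in placebo. If nobody is affected, nothing changes.

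**Step 4: why re-inclusion alone does not repair the AUCs.** The planning placebo AUC12-96 of 440 over 84 h is 440/84 = 5.24 per hour. Assume the same level from time 0. The average AUC0-24 is then 5.24 × 24 = 125.7 and the average AUC0-96 is 5.24 × 96 = 502.9. Take a failure with constant pain of 8 from time 0 who stops at hour 10 (both values assumed). Observed scores give 8 × 10 = 80; with a four-hour carry-forward to hour 14, 8 × 14 = 112. Either way the failure looks better than the average subject.

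**The case against.** The strongest reply is that this is a wording mismatch with little consequence. The study stopped early and no comparisons will be made. SAP 4.3 lists each subject's populations and tabulates mITT by group, and AUCs, PGA scores and rescue use are all listed by subject. A careful reader could see any exclusion. That limits the harm but does not remove it, because the summary tables would still be built on an outcome-dependent set.

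The 12-hour score is mandatory even at night. That protects subjects still being scored at hour 12, not those who stopped earlier under Protocol 5.4.3.

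For rescue use, discontinuation from efficacy is not the same status as mITT membership, and the endpoint-specific sentence in SAP 7.3.4 can be read as keeping everyone. This stands: it is not secure to say that every efficacy analysis loses these subjects.

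Two stronger readings are tempting and fail. A reader might infer that all early users of non-protocol rescue leave mITT. SAP section 3 treats them as discontinued from efficacy, but only for computing the analgesic endpoints. SAP 4.1 asks for a non-missing score, so a user still scored after hour 12 qualifies as written. A reader might also infer that the definition was narrowed after the sponsor's staff were unblinded in Stage 1. The SAP is Version 1.0 and cites Amendment 3, while the protocol supplied is Amendment 4. The Amendment 3 wording is not visible, so neither the fact nor the timing of a change can be shown.

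**Conclusion.** The point holds in limited form. SAP 4.1 is narrower than both protocol definitions, which also differ from each other, and the visible text does not explain it. It excludes a subject who stops scoring for lack of efficacy before hour 12. On its wording that subject's continuing PGA and rescue data go too, with rescue use subject to reconciliation with SAP 7.3.4.

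A reader might go further and compute a shift in the primary endpoint. With 12 placebo subjects at 440, removing one at 8 × 84 = 672 gives (5280 − 672)/11 = 418.9, a fall of 21.1; removing two gives (5280 − 1344)/10 = 393.6, a fall of 46.4. The arithmetic is right but the cause is not the mITT wording: the same values are missing under any of the three definitions, because SAP 7.1.1 does not impute them. The pain level, the number removed and their placement in placebo only are also assumptions.

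What remains is possible bias in descriptive PGA and rescue summaries, of up to a quarter of a planned dose group per excluded subject. The documents do not show that any of the 23 dosed subjects is affected. It should be corrected, since the correction is cheap.

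**What to change.** 1. Use the Protocol 10.3 definition (all randomized subjects who received study drug, as randomized) in SAP 4.1 and the Protocol Summary. Record the change in SAP section 12.
2. Summarize PGA and rescue use on all dosed subjects, and state that SAP 7.3.4 governs rescue use.
3. For each AUC endpoint, report by arm how many subjects have no computable AUC and why. This also covers a subject with a single score in the window, from which the trapezoid in SAP 7.3.1 cannot form an area. Do not present truncated AUCs as complete.
4. Add one sensitivity summary with a stated imputation for subjects who stop scoring for lack of efficacy, for example the last or worst score before stopping carried through the interval. The documents contain no such rule, so it has to be written.

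The cost is wording in two places, one count table and one sensitivity summary. The drawback is that the sensitivity result rests on an imputation assumption and should be labelled so.

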4.2 Safety Population

The Safety population will include all subjects exposed to any amount of study drug. All safety analyses will be performed using the safety population and be based upon the actual treatment received if different from that randomized.

4.3 Disposition of Subjects

All subjects and the populations for which they qualify will be listed. If a subject is randomized but does not complete the surgery or receive study drug, they will not be counted in any analyses. Subjects who are screened and who fail screening or withdraw consent prior to randomization or are randomized but not treated will be listed and summarized in total and by reason. Subjects who are randomized, subjects who are included in each study population (mITT, and Safety), subjects who are treated, subjects who complete follow-up (safety only and safety/efficacy), and subjects who withdraw early from the study and the reason for withdrawal will be summarized by treatment group and overall in a subject disposition summary table. Subjects who are discontinued from the efficacy portion of the study or who discontinue the study but agree to be followed for safety will also be presented.

[figure not shown]
4.4 Major Protocol Deviations

A protocol deviation is any noncompliance with the clinical trial protocol or Good Clinical Practice (GCP) requirements. All deviations will be addressed in study source documents and transcribed into the electronic case report form (eCRF). All protocol deviations will be designated as major or minor prior to database lock by the sponsor's medical monitor.

Sponsor: Bonti, Inc.
Protocol Number: EB001-ABD201

Statistical Analysis Plan Version 1.0
Effective Date: 07NOV2018

All protocol deviations will be presented in a by-subject listing. Any site-specific deviations noted by the clinical monitors will be documented in the final CSR.

6. MEASUREMENTS OF TREATMENT COMPLIANCE

Study medication exposure will be provided in a data listing. Because study medication is administered at the study center by trained study personnel, compliance with study medication is not expected to be an issue and no summary will be provided.

7. EFFICACY EVALUATION

7.1 Overview of Efficacy Analysis Issues

7.1.1 *Handling of Dropouts or Missing Data*

If a subject receives protocol specified rescue medication, a windowed LOCF imputation method will be used and the pre-rescue pain NPRS/NPRS-A score for each assessment (pain at rest, pain after walking) will be carried forward for 4 hours. Intermittent missing pain scores (due to subject sleeping, etc.) will not be imputed, and AUC will be calculated based on non-missing values.

In AUC analyses, no other imputation will be performed for subjects who have missing values due to early drop out. In addition, there will be no imputation of missing data for safety or other efficacy assessments.

7.1.2 *Assessment Time Windows*

Assessment times will be based on the nominal protocol-specified assessment times.

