## 10.5 Sample Size

Subjects will be allocated to receive either EB-001 or placebo in a 1:1 ratio in Cohorts 1-3, a 4:1 ratio in Cohort 4, a 2:1 ratio in Cohort 5, a 3:1 Ratio in Cohort 6, and a 5:1 ratio in Optional Cohort 7 in Stage 1 stratified by ethnicity (Hispanic and non-Hispanic) starting from Cohort 2. The planned total sample size in Stage 1 will be up to 40-58 subjects (up to 24-39 for EB-001 and up to 16-19 for placebo) (Figure 1). Optional Cohort 7 will be considered after dosing of subjects in Cohorts 1-6.

Subjects in each arm of Stage 2 will be randomly allocated to receive either EB-001 or placebo. The planned total sample size will be 66 subjects (44 for EB-001 and 22 for placebo) in Stage 2 stratified by ethnicity (Hispanic and non-Hispanic) (Figure 1).

Sample size of this study is not based on formal computations. However, 22 for active and 22 for placebo provide ~67% power. This power is based on one-sided alpha of 0.05, a mean baseline maximum pain score of 7.5, AUC12-96 ~440 with no drug effect, the delta AUC of 110 (drug and placebo difference), and SD of 170 AUC12-96.

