- Baseline value is defined as the last valid measurement prior to the start treatment administration.
- Change from baseline is defined as post-baseline value minus baseline value.
- Duration of an AE will be computed in hours in the first 96 hours during confinement and thereafter in days as the stop date of the event minus the start date plus 1. If reported as ongoing at the time of database lock, the stop date will be imputed as the date of the last visit or the last date of any AE for the subject in the database, whichever is later. Other missing dates will be imputed as described in [Table 8-1](#).
- The number of days in the study is computed as: [Date of study completion or withdrawal minus the date of treatment administration (Day 0)] + 1.
- If duplicate values are obtained at a given visit (e.g., repeated vital sign measurements), the last value will be used unless it is noted that the measurement was in error for that value. Values that compromise interpretation will not be used in summaries (e.g., values

that were obtained post-dose will not be summarized as pre-dose values).

- If a pre-rescue NPRS is recorded in the same minute as a rescue medication is recorded, the NPRS will be assumed to have occurred PRIOR to the administration of rescue.
 - If a subject experiences inadequate analgesic relief and takes non- protocol specified rescue medication, they will be treated as 'discontinued' from the efficacy portion of the study. The date/time of the discontinuation will be assumed to be the date/time of the start of non-protocol specified rescue captured on protocol deviations eCRF. Early discontinuation from the efficacy portion affects the computation of the analgesic endpoints only.

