7.3 Analysis Methods

7.3.1 AUC Outcomes

All AUC calculations will be done using the standard trapezoidal rule

$$AUC = \sum_{i=0}^x \left(\frac{NPRS_i + NPRS_{i+1}}{2} \right) * (T_{i+1} - T_i)$$

Where: $NPRS_i$ = NPRS at time i , and $(T_{i+1} - T_i)$ is the Time difference in hours between time i and time $i+1$. The AUC calculation of NPRS-A will be calculated using the same formula, substituting $NPRS_{-A_i}$ in place of $NPRS_i$.

In the event that protocol specified rescue medication is used during the time period of AUC calculation, for purposes of AUC calculation, the NPRS and/or NPRS-A score taken prior to the dispensation of rescue medication will be used as the NPRS and/or NPRS-A score for the following 4-hour period and the observed AUC score will be ignored.

The individual NPRS and NPRS-A scores through Day 5 (prior to discharge) will be presented graphically over time by cohort and presented in subject listings.

The computed AUCs will be listed for the individual subjects along with the respective endpoints that they were calculated on.

7.3.2 *NPRS and NPRS-A Outcomes*

The individual NPRS and NPRS-A outcomes after discharge will be summarized at each time point similar to the primary analysis.

7.3.3 *Patient Global Assessment (PGA) of Pain Control*

To assess pain control, each subject will be asked the following question: "Overall, how well your pain has been controlled during the last 24 hours?" at 96 ± 2 hours (Days 5), and on Days 8, 15, and 29 (EOS/ET), using a 4-point categorical scale (Poor (0), Fair (1), Good (2), Excellent (3)).

PGA summary tables will include the proportion of subjects with each score, by cohort and time point. PGA scores will be listed.

7.3.4 *Rescue Medication*

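### For subjects who stop scoring early, AUC12-96 is on the natural reading an unscaled partial sum, so stopping because of poor pain control is reported as less pain

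*SAP*

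**What the plan says.** - **Formula.** SAP 7.3.1: "All AUC calculations will be done using the standard trapezoidal rule". The formula printed there adds trapezoids of score times hours. It does not divide by the time observed, and its upper limit is left undefined.
- **Missing data.** SAP 7.1.1 carries the pre-rescue score forward for 4 hours after protocol-specified rescue and leaves intermittent gaps unimputed. It then states: "In AUC analyses, no other imputation will be performed for subjects who have missing values due to early drop out".
- **Who stops.** Under SAP section 3, a subject with inadequate relief who takes rescue outside the protocol counts as discontinued from efficacy from that time, and "Early discontinuation from the efficacy portion affects the computation of the analgesic endpoints only". Protocol 5.4.3 attributes exceeding the rescue limit to lack of efficacy. It keeps those subjects in safety follow-up and has them complete later assessments "with the exception of efficacy assessments as follows", where the list includes NPRS and NPRS-A. The SAP is written to Amendment 3; the amendment summary shows that this separate handling came in with Amendment 2.
- **Who is analysed.** SAP 4.1 admits to mITT any treated subject with a single NPRS score from 12 to 96 h.
- **What is reported.** SAP sections 1 and 3 plan descriptive summaries without tests, because the study ended after 23 subjects were randomised. AUCs are listed by subject, and continuous outcomes are summarised by treatment.

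**The concern.** A lower AUC means less pain. A sum that ends when scoring ends is lower the earlier the subject stops, and two of the routes to stopping are, in the documents' own terms, failures of pain control. The rule therefore moves those subjects' primary endpoint in the wrong direction. It is also uneven: protocol rescue holds the high pre-rescue score for 4 hours, while a failure serious enough to need other rescue contributes nothing afterwards.

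More failures on placebo would hide a benefit; more failures on a dose would make that dose look better. Protocol 10.5 and the protocol summary tie the efficacy data to signal-finding, and the summary adds dose selection for future studies, so misleading group means matter even without a test.

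**Working it through.** **1. The planning figures.** Protocol 10.5 states "22 for active and 22 for placebo provide ~67% power", with "This power is based on one-sided alpha of 0.05, a mean baseline maximum pain score of 7.5", "AUC12-96 ~440 with no drug effect" and "the delta AUC of 110 (drug and placebo difference), and SD of 170 AUC12-96".
- Noncentrality = 110 / (170 × √(2/22)) = 2.146. A one-sided 0.05 t-test on 42 df gives power 67.95%, which reproduces the stated figure.
- The window is 96 − 12 = 84 h, so 440/84 = 5.24 is the mean score with no drug effect. The planned active mean is 440 − 110 = 330. These figures are on the scale of a full 84-hour sum.

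**2. Gaps inside the window do no such harm.** A constant score of 6 at 12, 14, 16, 24 and 26 h gives 84 = 6 × 14, because the trapezoid spans the gap. The problem is the missing tail.

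**3. One early stopper.** Assume a constant score y, with scoring from 12 h to stop time T. The sum is y × (T − 12) and the shortfall is y × (96 − T). For y = 7.5 (Protocol 10.5's maximum pain score, used here as an assumption):

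| Stop (h) | Partial sum | Full value | Shortfall |
|---|---|---|---|
| 14 | 15 | 630 | 615 |
| 24 | 90 | 630 | 540 |
| 48 | 270 | 630 | 360 |
| 72 | 450 | 630 | 180 |

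The sum is below 330 for any stop before 12 + 330/7.5 = 56 h, and below 440 for any stop before 12 + 440/7.5 = 70.7 h. A 4-hour pre-rescue carry running past the stop adds at most 4 × 7.5 = 30 (40 at NPRS 10).

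**4. Effect on a group mean.** SAP 2.4.3 planned 4 active and 4 placebo subjects in each of Cohorts 1–3. This gives 4 per dose and, as an assumption, 12 pooled placebo subjects (23 were randomised, so it may be 11).
- Stop at 24 h: 540/12 = 45 (540/11 = 49.1); dose group of 4: 540/4 = 135.
- Stop at 48 h: 360/12 = 30; 360/4 = 90.
- Stop at 24 h with pain at the planning average of 5.24: the shortfall is 5.238 × 72 = 377, giving 377/12 = 31.4 and 377/4 = 94.3.

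**5. Effect on a difference of 110.** Assume stops at 24 h and NPRS 7.5.
- Placebo only: 5% stopping gives 110 − 27 = 83; 10% gives 110 − 54 = 56; 20% gives 110 − 108 = 2.
- Active only: 10% gives 110 + 54 = 164.
- Equal shares in both arms at the same pain level cancel in the difference, although both means are too low.

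**6. If the AUC were set to missing instead.** Take 12 placebo subjects with a true mean of 440, one of them at 630. The other 11 average (5,280 − 630)/11 = 422.7, a fall of 17.3. In a dose group of 4 with a true mean of 330, the other three average (1,320 − 630)/3 = 230, a fall of 100. This reading is also driven by outcome.

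**The case against.** The strongest reply is that truncation is inferred. No sentence says that a partial sum is reported as AUC12-96; the wording about computing from non-missing values sits with intermittent gaps, and declining to impute could also leave the AUC missing. That is fair. But a one-score entry rule for mITT and a formula that runs over whatever scores exist make the partial sum the natural reading, and step 6 shows that the alternative is not neutral.

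A reader might infer that failures score near zero and rank as the best responders. The documents do not support that. At NPRS 7.5 the sum is under 10% of 440 only for stops before about 17.9 h, and a stop at 72 h gives 450, above the no-effect mean. A subject with no score at or after 12 h leaves mITT altogether. A reader might also infer a reversed trial conclusion, but the SAP makes no comparison that could be reversed.

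Other points that stand:
- The documents give no stop rate, and the window falls within inpatient confinement.
- Protocol 5.4.2 asks for an NPRS at early termination before 96 h, which adds one score.
- Protocol 5.4.3 speaks of later visits and does not say outright that two-hourly inpatient scoring ends.
- Individual scores through Day 5 are plotted and listed, so a truncated profile can be seen. The summarised means would still carry it.

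**Conclusion.** The concern holds. As written, the rule gives subjects who stop because of poor pain control an AUC12-96 that is too low in proportion to the hours lost. Under the stated assumptions, one stop at 24 h moves a pooled placebo mean by about 31 to 49, and a dose-group mean by about 94 to 135, against a planned difference of 110. The direction across arms depends on who stops, which the documents do not report. The sizes rest on constant pain after stopping, an assumed placebo count and an assumed stop time; the 110 is Stage 2's planning value, used only as a yardstick. The damage is to listed and summarised AUCs, not to a p-value.

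A secondary point concerns AUC0-24 to AUC0-96. Time 0 is the end of dosing under anaesthesia, and scoring begins only once the subject is awake. No rule covers the interval before the first score, so later waking lowers these sums. This is not outcome-driven stopping, and no size is claimed for it.

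**What to change.** In SAP 7.1.1 and 7.3.1, before database lock:
- Do not report a raw partial sum as AUC12-96. For early stoppers, report the time-weighted mean NPRS over observed hours in the window, multiplied by 84.
- For subjects who stop for inadequate analgesia, non-protocol rescue or exceeding the rescue limit, add two sensitivity analyses: last score and worst score carried forward to 96 h.
- State how a subject with a single score in the window is handled; the observed time is then zero and the scaled value is undefined.
- List observed hours and stop reason beside each AUC.
- Scale AUC0-24 to AUC0-96 in the same way from the first awake score.

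The cost is a few lines of text and some programming. The downside is that scaling assumes pain after stopping equals the observed average. Carrying the worst score forward can err the other way by holding early post-operative pain at its peak, so it belongs in a sensitivity analysis and not in the main rule.
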